### 5.1.1 Screening and enrolment

After having obtained written informed consent from the participants the Principal Investigator will control and ensure that the inclusion and exclusion criteria of this study protocol are met (including weight and length measure), and complete the upper part of the child test form, attachment 3, covering background information on the child.

The enrolment can, but does not need to, be done on the same day as the actual test.

### 5.1.2 HF Validation test – Observations

1. The child's PT/OT is presented to the device and it's labelling and is asked to:
  - connect the battery charger to the battery charging port, and disconnect it.
  - adjust the seat and table height so that they are appropriate for the child.
  - adjust the speed of the device so that it is appropriate for the child.
  - place the child into the device.
  - if needed, adjust cushion and/or other support to ensure that the child is placed properly and safely.

The PI documents the observations on an observation form, attachment 1.

2. The Principal Investigator presents the device and labelling (including user manual) to the parent/guardian and PT/OT and performs a standard product training of the device.
3. The parent/guardian is presented to the device and it's labelling and is asked to:
  - connect the battery charger to the battery charging port, and release it.
  - adjust the seat and table height so that they are appropriate for the child.
  - adjust the speed of the device so that it is appropriate for the child.
  - place the child into the device.
  - if needed, adjust cushion and/or other support to ensure that the child is placed properly and safely.

The PI documents the observations on another observation form, attachment 1.

The activities above are derived from the risk-analysis of the device, performed prior to this test, and are performed by the secondary users, where the child is needed in order to perform them but does not play an active role.

One PT/OT may be the professional care-giver to more than one of the children included in the test. Step one above will only be performed once for an individual PT/OT.

4. As the child is placed in the device by the parent/guardian, the child is allowed to explore the device for 5 minutes. The child will be instructed to place their hand on the joystick and watch how he/she can move it. If the child does not initiate after a verbal prompt the Principal Investigator will place the child's hand on the joystick. The child test form, attachment 3, will be used to describe the child's actions and reactions.

If the child seems interested they may be placed in the device up to two times during the visit, with at least five minutes of rest in between. If the child shows signs of distress (such as crying) for at least one-minute, then they will be taken out of the device for a five-minute rest period. A new attempt will be made to place the child in the device. A maximum of three, one-minute attempts will be made to provide an opportunity for the child to use the device before this step is ended.

The Principal Investigator will use the observation form for secondary users to document observed user problems and use errors during the test, see attachment 1.

The Principal Investigator will complete two forms per test:

1. The child's PT/OT (performing the test without training)
2. The child's parent/guardian (performing the test with training)

The Principal Investigator will use a child test form for primary users to document observed user problems and user errors during the test as well as the ability to get the device in motion and the child's actions and reactions.

User errors performed during the tasks will be divided into three severity levels:

1. User experienced difficulties in performing the task but did not lead to harm
2. User performed an error that could have resulted in harm but never did
3. User performed an error that resulted in harm.

Details of the risk analysis performed in the preliminary analysis can be found in the Human Factors validation plan ES1692.

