## 5.1 Methodology

The introduction of the device to the children and caregivers will, once the product is commercially available, be performed by a PT/OT. Supplemental instructions will be given in the user's manual. In order to validate that the device is safe to use also without having received any training, the first observational part of the study will be performed in three steps.

1. To simulate an initial encounter with the device for a PT/OT where the device may be handled without any additional instructions, the child's PT/OT will first perform the test tasks untrained. The PT/OT will be provided with the User's manual but may not be prompted to use it for written information of the product.
2. In standard of care, after having learned how to use the device, a PT/OT would show the parent/guardian how to operate the device. In step two, the Principal Investigator will train the parent/guardian and the PT/OT on the device (standard product training) supported by references to the Users' manual.
3. The parent/guardian performs the test tasks, supported with the Users' manual and PT/OT or Principal Investigator.

The Principal Investigator will provide arm's length supervision throughout all steps of the study to ensure the safety of all participants.

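### In step 1 the untrained PT/OT is told which adjustments to make, so the run is weak evidence on whether a first-time user would leave one out

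*Protocol*

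**What the plan says.** Section 5.1 (Methodology) gives the reason for the three-step observation: "In order to validate that the device is safe to use also without having received any training". Step 1 serves that aim. Its purpose is "To simulate an initial encounter with the device for a PT/OT where the device may be handled without any additional instructions", and for this "the child's PT/OT will first perform the test tasks untrained". The manual is at hand, but its use is left to the user: "The PT/OT will be provided with the User's manual but may not be prompted to use it".

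Section 5.1.2 (Observations) sets out how step 1 is run: "The child's PT/OT is presented to the device and it's labelling and is asked to" do five things, given as unnumbered bullets. These are to connect and disconnect the charger, to set seat and table height to suit the child, to "adjust the speed of the device so that it is appropriate for the child", to place the child, and "if needed, adjust cushion and/or other support to ensure that the child is placed properly and safely". The section adds that these activities come from the device's risk analysis, and that each PT/OT does step 1 once only.

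Step 3 puts nearly the same list to the parent or guardian, but after standard product training and with help available: "The parent/guardian performs the test tasks, supported with the Users' manual and PT/OT or Principal Investigator".

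**The concern.** A person who meets the device without instruction must find out from the device, its labelling or the manual that height and speed can be set, and that they should be set for this child. Whether the interface conveys this is part of what a first-encounter simulation should show. In step 1 the request itself supplies it.

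Failing to make a safety-relevant adjustment at all is a plausible error in an untrained user, and it is the error that naming the task suppresses. Section 6.1 will use the results to judge whether intended users can use the device free of serious use errors or problems. A clean step 1 would mainly show that PTs/OTs can carry out tasks they have been asked for. It would say little about whether they would have thought to do them.

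**Working it through.** No formula applies, because the protocol states no rate, target or acceptance figure for this step. The check is to set the passages side by side.

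1. **Condition to be simulated (5.1).** The user is untrained and handles the device without additional instructions. The manual is available, but the user is not steered to it. The design therefore takes some care to avoid cueing.

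2. **Condition delivered (5.1.2, step 1).** The user is untrained and is asked for five named tasks. For height and speed, the request conveys that the adjustment exists, that it should be made, and that the aim is suitability for the child. It does not convey the method or the setting.

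3. **What stays observable.**
   - Errors in how a task is done, such as a wrong setting or a poor placement, can be seen as before.
   - So can partial omissions, such as setting the seat but not the table.
   - The cushion or support task is conditional, so the user still decides whether it is needed and may wrongly leave it out.
   - The three severity levels in 5.1.2 exclude no type of error. An omission that could have caused harm fits level 2.

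4. **What is weakened.** Omission of a whole task because the user did not know of it, chiefly height and speed, is cued away in most cases.

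5. **Whether another step recovers the information.** Section 5.1.2 lists two observation forms per test, one for the PT/OT without training and one for the parent or guardian with training. Step 1 is thus the only untrained caregiver run, and a PT/OT is not observed in it a second time. Nothing later in the protocol shows unprompted behaviour before training.

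6. **Size.** A figure would need the number of PTs/OTs and the rate at which unprompted users skip an adjustment. Neither is given. The 10 in section 4.3 is child/parent pairs per clinic, and section 5.1.2 lets one PT/OT care for several of the 30 children. The direction of the bias is clear, but its amount is not.

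**The case against.** The strongest reply is that the two sections do not conflict. The stated aim is safety without training, and the sentence about additional instructions goes on to say that the PT/OT performs the test tasks untrained. On that reading, additional instructions means training or a pointer to the manual, and both are withheld. Section 5 defines the study as observing performance of critical and some non-critical tasks, so asking for tasks fits the declared design. Naming a task is not teaching it. In addition, Attachment 1 and the human factors validation plan ES1692 are not shown and may settle how tasks are presented.

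Much of this stands. There is tension between the simulation aim and the task request, but no outright contradiction, and the unseen documents could narrow the gap. The reply does not remove the point. Handling without additional instructions is a stricter condition than being untrained, and the protocol's own text has the user asked for each task. Performing the test tasks does not require announcing them: an observer can score the same five from a broader request.

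A reader might go further and infer that omission and sequence errors cannot occur at all. The text does not support that. The bullets carry no numbers, nothing says that they are read out one at a time or that an order is enforced, and a user can still forget an item or place the child first. Nor does the argument extend to step 3. That run follows training and is supported, and it was never meant as a first encounter.

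**Conclusion.** The point holds for step 1 only. Naming the height and speed adjustments and their goal makes whole-task omission less likely and leads to its under-detection. A clean step 1 is therefore weak evidence on that error type, and the bias favours the device. Evidence on how well tasks are performed is not affected. The change is worth making, because this is the only untrained caregiver run, the tasks come from the risk analysis, and the remedy is cheap.

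The conclusion assumes that investigators present the tasks as section 5.1.2 words them, and that neither Attachment 1 nor ES1692 says otherwise. No numerical size can be attached, and any probability of seeing an omission would rest on invented inputs.

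**What to change.** In section 5.1.2, step 1, replace the task-by-task request with goal-level requests, for example: *prepare the device for this child and place the child in it*, and *charge the device*. Keep the five listed tasks as the observer's checklist. Score each as done unprompted and correctly, done incorrectly, or omitted. Prompt only after an omission, under the arm's-length supervision already provided for in section 5.1, so that every task is still observed. Record an omitted or prompted task as a use error and grade it on the existing three-level scale. For the conditional cushion or support task, score an omission only where the adjustment was needed. Leave step 3 as it is.

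The cost is protocol wording, a scoring column on the observation form if it has none, and slightly longer sessions. No participants or staff are added. One limit remains: where the investigator steps in for safety before the child is placed, the error is recorded as an omission needing a prompt and does not run its course. If the sponsor keeps the present request, the validation report should state that step 1 does not test whether untrained users would make these adjustments unasked.

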### **5.1.3 HF Validation test – Interviews**

After the tasks in 5.1.2 have been performed, the Principal Investigator will interview the child's parent/guardian and PT/OT, in order to collect their perspectives of the tasks, to complement the task performance observations. An interview form, attachment 2, will be used.

## **6 Reporting results**

The test data will consist of:

1. Completed observation forms
2. Completed interview forms
3. Completed child test forms

### **6.1 Data analysis**

After completion of the human factors validation testing, the results of the observations and interviews will be analyzed qualitatively and quantitatively to determine if the design of the

device can be used by the intended users without serious use errors or problems. The results will be summarized in a human factors validation report.

## 8 Attachments

### **Attachment 1 Observation form**

Observation form, HF validation test protocol 06 August 2018

### **Attachment 2 Interview form**

Interview form, HF validation test protocol 06 August 2018

### **Attachment 3 Child test form**

Child test form, HF validation test protocol 06 August 2018

### **Attachment 4, Recruitment script**

Recruitment script, HF validation test protocol 06 August 2018
